10.7. Appendix 7: Kidney Safety: Monitoring Guidelines

10.7.1. Laboratory Assessment of Change in Kidney Function and Detection of Kidney Injury

Standard kidney safety monitoring requires assessment of baseline and postbaseline serum creatinine (SCr measurement to estimate glomerular filtration rate [SCr-based eGFR] or eCrCl]. Baseline and postbaseline serum SCys makes it feasible to distinguish AKI from other causes of SCr increase. If SCr increase is confirmed after baseline, then reflex measurement of SCys is indicated to estimate the combined SCr-SCys eGFR calculation (for adults only).

Regardless of whether kidney function monitoring tests are required as a routine safety monitoring procedure in the study, if the investigator or sponsor deems it necessary to further assess kidney safety and quantify kidney function, then these test results should be managed and followed per standard of care.

10.7.2. Age-Specific Kidney Function Calculation Recommendations

10.7.2.1. Adults (18 Years and Above)—2021 CKD-EPI Equations

2021 CKD-EPI SCr Only	SCr (mg/dL)	SCys	Recommended eGFR Equation
·	1 0 /	(mg/L)	GER 142 (GG (0.7) 0.241 (0.0020) Am
Female	if ≤0.7	NA	$eGFR = 143 \times (SCr/0.7)^{-0.241} \times (0.9938)^{Age}$
Female	if >0.7	NA	$eGFR = 143 \times (SCr/0.7)^{-1.200} \times (0.9938)^{Age}$
Male	if ≤0.9	NA	$eGFR = 142 \times (SCr/0.9)^{-0.302} \times (0.9938)^{Age}$
Male	if >0.9	NA	$eGFR = 142 \times (SCr/0.9)^{-1.200} \times (0.9938)^{Age}$
2021 CKD-EPI	SCr	SCys	Recommended eGFR Equation
SCr-SCys	(mg/dL)	(mg/L)	
Combined			
Female	if ≤0.7	if≤0.8	$eGFR = 130 \times (SCr/0.7)^{-0.219} \times (SCys/0.8)^{-0.323} \times (0.9961)^{Age}$
Female	if ≤0.7	if>0.8	$eGFR = 130 \times (SCr/0.7)^{-0.219} \times (SCys/0.8)^{-0.778} \times (0.9961)^{Age}$
Female	if >0.7	if ≤0.8	$eGFR = 130 \times (SCr/0.7)^{-0.544} \times (SCys/0.8)^{-0.323} \times (0.9961)^{Age}$
Female	if >0.7	if>0.8	$eGFR = 130 \times (SCr/0.7)^{-0.544} \times (SCys/0.8)^{-0.778} \times (0.9961)^{Age}$
Male	if ≤0.9	if≤0.8	$eGFR = 135 \times (SCr/0.9)^{-0.144} \times (SCys/0.8)^{-0.323} \times (0.9961)^{Age}$
Male	if ≤0.9	if>0.8	$eGFR = 135 \times (SCr/0.9)^{-0.144} \times (SCys/0.8)^{-0.778} \times (0.9961)^{Age}$
Male	if >0.9	if ≤0.8	$eGFR = 135 \times (SCr/0.9)^{-0.544} \times (SCys/0.8)^{-0.323} \times (0.9961)^{Age}$
Male	if >0.9	if>0.8	$eGFR = 135 \times (SCr/0.9)^{-0.544} \times (SCys/0.8)^{-0.778} \times (0.9961)^{Age}$
		So	ource:9

10.7.3. Adverse Event Grading for Kidney Safety Laboratory Abnormalities

AE grading for decline in kidney function (ie, eGFR or eCrCl) will be according to KDIGO criteria. 10

10.8. Appendix 8: ECG Findings of Potential Clinical Concern

ECG Findings That May Qualify as AEs

- Marked sinus bradycardia (rate <40 bpm) lasting minutes.
- New PR interval prolongation >280 ms.
- New prolongation of QTcF to >480 ms (absolute) or by ≥ 60 ms from baseline.
- New-onset atrial flutter or fibrillation, with controlled ventricular response rate: ie, rate <120 bpm.
- New-onset type I second-degree (Wenckebach) AV block of >30 seconds' duration.
- Frequent PVCs, triplets, or short intervals (<30 seconds) of consecutive ventricular complexes.

ECG Findings That May Qualify as SAEs

- QTcF prolongation >500 ms.
- New ST-T changes suggestive of myocardial ischemia.
- New-onset LBBB (QRS complex>120 ms).
- New-onset right bundle branch block (QRS complex>120 ms).
- Symptomatic bradycardia.
- Asystole:
 - In awake, symptom-free participants in sinus rhythm, with documented periods of asystole ≥3.0 seconds or any escape rate <40 bpm, or with an escape rhythm that is below the AV node.
 - In awake, symptom-free participants with atrial fibrillation and bradycardia with 1 or more pauses of at least 5 seconds or longer.
 - Atrial flutter or fibrillation, with rapid ventricular response rate: rapid = rate >120 bpm.
- Sustained supraventricular tachycardia (rate >120 bpm) ("sustained" = short duration with relevant symptoms or lasting >1 minute).

- Ventricular rhythms >30 seconds' duration, including idioventricular rhythm (HR <40 bpm), accelerated idioventricular rhythm (HR >40 bpm to <100 bpm), and monomorphic/polymorphic ventricular tachycardia (HR >100 bpm [such as torsades de pointes]).
- Type II second-degree (Mobitz II) AV block.
- Complete (third-degree) heart block.

ECG Findings That Qualify as SAEs

- Change in pattern suggestive of new myocardial infarction.
- Sustained ventricular tachyarrhythmias (>30 seconds' duration).
- Second- or third-degree AV block requiring pacemaker placement.
- Asystolic pauses requiring pacemaker placement.
- Atrial flutter or fibrillation with rapid ventricular response requiring cardioversion.
- Ventricular fibrillation/flutter.
- At the discretion of the investigator, any arrhythmia classified as an adverse experience.

The enumerated list of major events of potential clinical concern are recommended as "alerts" or notifications from the core ECG laboratory to the investigator and Pfizer study team, and not to be considered as all-inclusive of what to be reported as AEs/SAEs.

10.9. Appendix 9: Protocol Amendment History

The protocol amendment summary of changes table for the current amendment is located directly before the TOC. The protocol amendment summary of changes tables for past amendment(s) can be found below:

Amendment 1 (29 September 2022)

Overall Rationale for the Amendment: use precautionary sentinel dosing in dose escalation to mitigate potential unpredicted risks in FIH study

Section # and Name	Description of Change	Brief Rationale	Substantial or Nonsubstantial
Section 1.1 (Synopsis), Section 1.2 (Schema), Section 4.1 (Overall Design), Section 6.6.1 (Dose Escalation and Stopping Rules)	Added description wording of precautionary sentinel dosing in Overall Design of synopsis, Schema and Overall Design.	To describe sentinel dosing	Substantial
Section 2.3 (Benefit/Risk Assessment),	Mentioned the use of precautionary sentinel dosing.	To describe sentinel dosing	Substantial
Section 4.2 (Scientific Rationale for Study Design)	Added the scientific rationale for precautionary sentinel dosing.	To provide rationale for precautionary sentinel dosing	Substantial
Title page and Section 1.1 (Synopsis)	Added US IND number	To provide the US IND number	Nonsubstantial

10.10. Appendix 10: Abbreviations

The following is a list of abbreviations that may be used in the protocol.

Abbreviation	Term
Abs	absolute
ADL	activity/activities of daily living
AE	adverse event
AKI	acute kidney injury
ALT	alanine aminotransferase
ANOVA	analysis of variance
AST	aspartate aminotransferase
AUC	area under the plasma concentration-time curve
AUC _{24,u}	unbound AUC over 24 hours
AUEC	area under the effect curve
AV	atrioventricular
Ave	average
AxMP	auxiliary medicinal product
BBS	Biospecimen Banking System
BCAA	branched-chain amino acid
BCKA	branched-chain ketoacid
BCKDH	branched-chain ketoacid dehydrogenase
BCKDHA	branched-chain ketoacid dehydrogenase E1 subunit alpha
BCRP	breast cancer resistance protein
BDK	branched chain ketoacid dehydrogenase kinase
BID	twice a day
BMI	body mass index
BP	blood pressure
bpm	beats per minute
BUN	blood urea nitrogen
Cave	average concentration
CBC	complete blood count
Ceff	efficacious concentration
CFR	code of Federal Regulations
CIOMS	council for International Organizations of Medical Sciences
CK	creatine kinase
CKD-EPI	chronic kidney disease epidemiology
CL	clearance
C _{last}	last quantifiable concentration
C _{max}	maximum concentration
$C_{\text{max,u}}$	unbound C _{max}
CO ₂	carbon dioxide (bicarbonate)
COVID-19	coronavirus disease 2019
C_p	total concentration

Abbreviation	Term
CRF	case report form
CRO	contract research organization
CRU	clinical research unit
CSR	Clinical Study Report
CT	clinical trial
CTIS	Clinical Trial Information System
CYP	cytochrome P450
DCT	data collection tool
DDI	drug-drug interaction
DICI	drug-induced cholestatic injury
DIKI	drug-induced kidney injury
DILI	drug-induced liver injury
С	3 7
DNA	deoxyribonucleic acid
EC	ethics committee
ECC	emergency contact card
ECCS	extended clearance classification system
ECG	electrocardiogram or electrocardiography
FDA	Food and Drug Administration
eCrCl	estimated creatinine clearance
eCRF	electronic case report form
EDB	exposure during breastfeeding
E-DMC	external data monitoring committee
EDP	exposure during pregnancy
EDR	extemporaneous dispensing record
eGFR	estimated glomerular filtration rate
EMA	European Medicines Agency
EP	extemporaneously prepared
eSAE	electronic serious adverse event
ET	early termination
EU	European Union
EudraCT	European Union Drug Regulating Authorities Clinical Trials
	(European Clinical Trials Database)
F	bioavailability
fa	fraction absorbed
fg	fraction escaping intestinal metabolism
FSH	follicle-stimulating hormone
fu	fraction unbound
GCP	Good Clinical Practice
GGT	gamma-glutamyl transferase
GLP	Good Laboratory Practice
Hb	hemoglobin

Abbreviation	Term
HBcAb	hepatitis B core antibody
HBsAb	hepatitis B surface antibody
HBsAg	hepatitis B surface antigen
HCVAb	hepatitis C antibody
HF	heart failure
HIV	human immunodeficiency virus
HR	heart rate
HRT	hormone replacement therapy
IADR	idiosyncratic drug reaction
IB	Investigator's Brochure
IC ₅₀	half maximal inhibitory concentration
ICD	informed consent document
ICH	International Council for Harmonisation of Technical
	Requirements for Pharmaceuticals for Human Use
ID	identification
Ile	isoleucine
IMP	investigational medicinal product
IND	Investigational New Drug
INR	international normalized ratio
IPAL	Investigational Product Accountability Log
IRB	Institutional Review Board
IV	intravenous(ly)
K	Proportionality constant for Bedside and Modified Schwartz
	Equations (kidney function)
K ₂ EDTA	K ₂ dipotassium ethylenediaminetetraacetic acid
KDIGO	Kidney Disease Improving Global Outcomes
KIC	ketoleucine
KIV	ketovaline
KMV	ketoisoleucine
LBBB	left bundle branch block
Leu	namely leucine
LFT	liver function test
LVSP	peak left ventricular systolic pressure
MCH	mean corpuscular hemoglobin
MCHC	mean corpuscular hemoglobin concentration
MCV	mean corpuscular volume
MMTT	mixed meal tolerance test
MQI	medically qualified individual
NA	not applicable
NAFLD	non-alcoholic fatty liver disease
NASH	non-alcoholic steatohepatitis
NHP	nonhuman primate

Abbreviation	Term
NIMP	noninvestigational medicinal product
NOAEL	no observed adverse effect level
NOEL	no observed effect level
OATP	organic-anion-transporting polypeptides
CCI	
PBPK	physiologically based pharmacokinetic
PCRU	Pfizer Clinical Research Unit
PD	pharmacodynamic(s)
PE	physical examination
PI	principal investigator
PK	pharmacokinetic(s)
PO	by mouth
PR	pulse rate
PSSA	Pfizer's Serious Adverse Event Submission Assistant
PT	prothrombin time
PVC	premature ventricular contraction/complex
QTc	corrected QT interval
QTcF	QTc corrected using Fridericia's formula
qual	qualitative
RBC	red blood cell
RNA	ribonucleic acid
RRCK	Ralph Russ canine kidney
SAD	single ascending dose
SAE	serious adverse event
SAP	Statistical Analysis Plan
SARS-CoV-2	severe acute respiratory syndrome coronavirus 2
SBP	systolic blood pressure
SCr	serum creatinine
SCys	serum cystatin C
SM	safety margin
SoA	schedule of activities
SOP	standard operating procedure
SPF	sun protection factor
SRSD	single reference safety document
SUSAR	Suspected Unexpected Serious Adverse Reaction
$t_{1/2}$	terminal elimination half-life
T bili	total bilirubin
THC	tetrahydrocannabinol
UACR	urine albumin/creatinine ratio
UGT	uridine 5'-diphospho-glucuronosyltransferase
ULN	upper limit of normal
US	United States

Abbreviation	Term
UTI	urinary tract infection
UV	ultraviolet
Val	valine
V_{ss}	volume of distribution at steady state
WBC	white blood cell
WOCBP	woman/women of childbearing potential

# 1. VERSION HISTORY

**Table 1.** Summary of Changes

Version/ Date	Associated Protocol Amendment	Rationale	Specific Changes
1 07 Nov 2022	Original: 02Sep2022	N/A	N/A
	Amendment 1 29 Sept 2022		
	CCI		

#### 2. INTRODUCTION

PF-07328948 is a small molecule allosteric inhibitor/degrader of BDK that is currently being developed as an oral therapy to treat heart failure.

Tissue and/or plasma BCAA and/or BCKA levels are elevated in various disease states including heart failure, type 2 diabetes mellitus, NAFLD/NASH, and obesity. Furthermore, elevated BCAA levels in HF are associated with a loss of the BCAA catabolic machinery, suggesting that the BCKDH pathway, involved in BCAA and BCKA catabolism, is dysregulated in cardiometabolic disease indications. Because inhibitory phosphorylation of BCKDH by BDK reduces BCAA catabolism, a BDK inhibitor would reduce BCKDH phosphorylation, thereby increasing BCAA and BCKA catabolism and reducing the elevated levels of BCAAs and BCKAs associated with several cardiovascular and metabolic diseases.

PF-07328948 is an orally administered, small molecule, potent allosteric BDK inhibitor that inhibits BCKDH phosphorylation in vitro and has consistently demonstrated robust, dose- and time-dependent BCAA and BCKA lowering in plasma and in mouse, rat and/or dog. In addition,

These improvements were concomitant with reduced pBCKDH and BDK levels in heart and kidney as well as reduced plasma BCAA and BCKA levels.

This study will be the first time PF-07328948 is administered to humans. The purpose of the study is to evaluate the safety, tolerability, plasma PK and PD of PF-07328948 following administration of escalating, single, oral doses to healthy adult participants.

This statistical analysis plan (SAP) provides the detailed methodology for summary and statistical analyses of the data collected in this study - Study C4921001. This document may modify the plans outlined in the protocol; however, any major modifications of the primary endpoint definition or its analysis will also be reflected in a protocol amendment.

Text in *italics* is taken directly from the protocol.

2.1. Modifications to the Analysis Plan Described in the Protocol

N/A.

# 2.2. Study Objectives, Endpoints, and Estimands

Type	Objectives	Endpoints	Estimand
	Primary:	Primary:	
Safety	To evaluate the safety and tolerability of single ascending doses of PF-07328948 administered orally to healthy adult participants.	Assessment of adverse events, clinical safety laboratory tests, vital signs, continuous cardiac monitoring, 12-lead electrocardiograms, and physical examinations.	N/A
	Secondary:	Secondary:	
PK	To evaluate the pharmacokinetics of PF- 07328948 following single doses of PF- 07328948 administered orally to healthy adult participants.	• PK parameters derived from plasma PF-07328948 concentrations: C max , T max , AUC last , and if data permit, AUC inf , and t ½ .	N/A
	Tertiary/Exploratory:	Tertiary/Exploratory:	
PK	To evaluate additional pharmacokinetic parameters of PF-07328948 following single doses of PF-07328948 administered orally to healthy adult participants.	• Additional PK parameters derived from plasma PF-07328948 concentrations: $C_{max}(dn)$ , $AUC_{last}(dn)$ and if data permit $AUC_{inf}(dn)$ , $CL/F$ and $V_z/F$ .	N/A
CI			
PK	To evaluate the effect of food (eg, a protein-rich meal such as MMTT), if administered, on the plasma PK of PF-07328948 following single dose of PF-07328948 administered orally to healthy adult participants.	• PK parameters derived from plasma PF-07328948 concentrations after MMTT: C max , T max , AUC last , and if data permit, AUC inf , and t s .	N/A

#### 2.3. Study Design

This is a randomized, investigator- and participant-blind, sponsor-open, placebo-controlled, first-in-human, single ascending oral dose, 4-period, sequential, crossover study of PF-07328948 administered to healthy adult participants.

The first 2 cohorts are planned, and the third cohort is optional. In each period, participants will be randomized to either PF-07328948 or placebo in a ratio of 3:1. Each participant is planned to undergo up to 4 treatment periods receiving up to 4 doses of PF-07328948 and up to 2 placebo.

Precautionary sentinel dosing will be used in any period evaluating escalating doses of PF-07328948 and may be omitted for periods when repeating a dose level or administering a lower dose level than previously evaluated. For periods with sentinel dosing, 2 participants (1 receiving PF-07328948 and 1 receiving placebo) will be dosed initially before the remaining participants of that period are dosed. Safety and tolerability data through at least 24 hours post-dose for the sentinel participants will be reviewed prior to dosing the remaining participants of that period.

In each cohort, a washout interval of at least 7 days will be introduced between subsequent doses.

Based on the review of emerging safety, tolerability, and PK data (and PD data if available) in Cohorts 1 and 2, the optional third cohort may enroll 8 participants (crossover, placebo-controlled design) to explore additional doses, to repeat a dose, to evaluate split dosing, or to investigate food effects on PK CCI

The effect of a high-protein meal on safety, tolerability, PK exposure, may be assessed in at least 1 period within Cohort 2 and/or Cohort 3.

If a participant drops out before completing all study periods within a cohort, or withdraws for a reason unrelated to safety, the participant may be replaced at the discretion of the investigator and sponsor. The replacement participant(s) may or may not be required to complete all periods of the cohort in which they are participating at the discretion of the investigator and sponsor.

**Number of Participants:** Approximately 24 healthy adult participants (up to 3 cohorts of approximately 8 participants each) will be enrolled in this study.

[figure not shown]

Figure 1. Study Design Schemaa,b,c

- a. Doses shown for each cohort except the starting dose in Cohort 1 are planned doses and may be modified based on emerging data from previous cohorts. Similarly, assignment to study intervention may be modified. n represents number of participants
- b. Effect of food (eg, a protein-rich meal such as MMTT) may be evaluated in at least 1 period of Cohort 2 (eg, P3) and/or Cohort 3
- c. In the first period in each cohort (with red box) and the first period of assessment of food effect in any cohort (eg, P3 in Cohort 2 with red box), participants will be admitted on Day -2 and time-matched biomarker assessment will be collected on Day -1.
- d. Precautionary sentinel dosing will be used in any period evaluating escalating doses of PF-07328948. For such periods, 2 participants (1 receiving PF-07328948 and 1 receiving placebo) will be dosed initially before the remaining participants of that period are dosed. Safety and tolerability data through at least 24 hours post-dose for the sentinel participants will be reviewed prior to dosing the remaining participants of that period. Sentinel dosing may be omitted when repeating a dose level or administering a lower dose level than previously evaluated.

# 3. ENDPOINTS AND BASELINE VARIABLES: DEFINITIONS AND CONVENTIONS

#### 3.1. Primary Endpoint(s)

As listed in Section 2.2, the primary endpoints are related to safety/tolerability and are described in Section 3.5.

#### 3.2. Secondary Endpoint(s)

As listed in Section 2.2, the secondary endpoints are related to PK and are described in Section 3.3.1.

#### 3.3. Other Endpoint(s)

#### 3.3.1. PK Endpoints

Blood samples for PK analysis of PF-07328948 will be taken according to the Schedule of Activities given in the protocol.

The plasma PK parameters for PF-07328948, following oral dose administration, will be derived from the plasma concentration-time profiles using standard noncompartmental

methods as detailed in Table 2, as data permit. Table 2 shows the analysis scale and method for each parameter.

In all cases, actual PK sampling times will be used in the derivation of PK parameters. In the case that actual PK sampling times are not available, nominal PK sampling time will be used in the derivation of PK parameters.

Table 2. Plasma PF-07328948 PK Parameters

Parameter	Definition	Method of Determination	Analysis Scale	PF-07328948
AUClast	Area under the plasma concentration-time curve from time 0 to the time of the C last	Linear/Log trapezoidal method	ln	D,A
AUCinf*	Area under the plasma concentration-time curve from time 0 extrapolated to infinite time	AUClast + (Clast*/kel), where Clast* is the predicted plasma concentration at the last quantifiable timepoint estimated from the log-linear regression analysis	ln	D,A
Стах	Maximum plasma concentration	Observed directly from data	ln	D,A
Tmax	Time for Cmax	Observed directly from data as time of first occurrence	R	D
t ½ *	Terminal elimination half-life	Loge(2)/kel, where kel is the terminal phase rate constant calculated by a linear regression of the log-linear concentration-time curve. Only those data points judged to describe the terminal log-linear decline will be used in the regression.	R	D
CL/F*	Apparent clearance	Dose/AUCinf	ln	D
Vz/F*	Apparent volume of distribution	Dose/(AUC inf k el )	ln	D
AUClast(dn)	Dose-normalized AUClast	AUClast/Dose	ln	D
AUCinf(dn)*	Dose-normalized AUCinf	AUCinf/Dose	ln	D
Cmax(dn)	Dose-normalized Cmax	Cmax/Dose	ln	D

[figure not shown]
Key: D=displayed with descriptive statistics,

ln=natural-log transformed, R=raw (untransformed),

A=analysed using a statistical model (for specific treatment groups for evaluating food effect)

 $T_{last}$  will also be provided as a support parameter for AUClast.  $T_{last}$  values will only be listed and not summarized.

\*=if data permits, dn = normalized to a 1mg PF-07321332 dose

#### 3.4. Baseline Variables

Baseline for PD endpoints, laboratory data, vital signs and ECG are defined in Sections 3.3.2, 3.5.2, 3.5.3 and 3.5.4, respectively.

### 3.5. Safety Endpoints

#### 3.5.1. Adverse Events

An adverse event is considered a Treatment-Emergent Adverse Event (TEAE) if the event started during the effective duration of treatment. All events that start on or after the first dosing day and time/start time, if collected, but before the end of the study will be flagged as TEAEs. The algorithm will not consider any events that started prior to the first dose date.

A 3-tier approach for summarizing adverse events (AEs) will not be used due to the low number of participants planned to be recruited.

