8.4.1. Time Period and Frequency for Collecting AE and SAE Information

The time period for actively eliciting and collecting AEs and SAEs ("active collection period") for each participant begins from the time the participant provides informed consent, which is obtained before undergoing any study-related procedure and/or receiving study intervention), through and including a minimum of 28 calendar days, except as indicated below, after the last administration of the study intervention.

Follow-up by the investigator continues throughout the active collection period and until the AE or SAE or its sequelae resolve or stabilize at a level acceptable to the investigator.

When a clinically important AE remains ongoing at the end of the active collection period, follow-up by the investigator continues until the AE or SAE or its sequelae resolve or stabilize at a level acceptable to the investigator and Pfizer concurs with that assessment.

For participants who are screen failures, the active collection period ends when screen failure status is determined.

If the participant withdraws from the study and also withdraws consent for the collection of future information, the active collection period ends when consent is withdrawn.

If a participant permanently discontinues or temporarily discontinues study intervention because of an AE or SAE, the AE or SAE must be recorded on the CRF and the SAE reported using the CT SAE Report Form.

Investigators are not obligated to actively seek information on AEs or SAEs after the participant has concluded study participation. However, if the investigator learns of any SAE, including a death, at any time after a participant has completed the study, and they consider the event to be reasonably related to the study intervention, the investigator must promptly report the SAE to Pfizer using the CT SAE Report Form.

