10.3.1. Definition of AE

AE Definition

- An AE is any untoward medical occurrence in a patient or clinical study participant, temporally associated with the use of study intervention, whether or not considered related to the study intervention.
- Note: An AE can therefore be any unfavorable and unintended sign (including an abnormal laboratory finding), symptom, or disease (new or exacerbated) temporally associated with the use of study intervention.

Events Meeting the AE Definition

- Any abnormal laboratory test results (hematology, clinical chemistry, or urinalysis) or other safety assessments (eg, ECG, radiological scans, vital sign measurements), including those that worsen from baseline, considered clinically significant in the medical and scientific judgment of the investigator. Any abnormal laboratory test results that meet any of the conditions below must be recorded as an AE:
 - Is associated with accompanying symptoms;
 - Requires additional diagnostic testing or medical/surgical intervention;
 - Leads to a change in study dosing (outside of any protocol-specified dose adjustments) or discontinuation from the study, significant additional concomitant drug treatment, or other therapy.
- Exacerbation of a chronic or intermittent preexisting condition, including an increase in either frequency and/or intensity of the condition.
- New condition detected or diagnosed after study intervention administration, even though it may have been present before the start of the study.
- Signs, symptoms, or the clinical sequelae of a suspected drug-drug interaction.
- Signs, symptoms, or the clinical sequelae of a suspected overdose of either study intervention or a concomitant medication. Overdose per se will not be reported as an AE or SAE unless it is an intentional overdose taken with possible suicidal/self-harming intent. Such overdoses should be reported regardless of sequelae.

Events NOT Meeting the AE Definition

- Any clinically significant abnormal laboratory findings or other abnormal safety assessments that are associated with the underlying disease, unless judged by the investigator to be more severe than expected for the participant's condition.
- The disease/disorder being studied or expected progression, signs, or symptoms of the disease/disorder being studied, unless more severe than expected for the participant's condition.
- Medical or surgical procedure (eg, endoscopy, appendectomy): the condition that leads to the procedure is the AE.

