^{***} Environmental or occupational exposure: AEs or SAEs associated with occupational exposure are reported to Pfizer Safety using the CT SAE Report Form.

- It is **not** acceptable for the investigator to send photocopies of the participant's medical records to Pfizer Safety in lieu of completion of the CT SAE Report Form/AE or SAE CRF page.
- There may be instances when copies of medical records for certain cases are requested by Pfizer Safety. In this case, all participant identifiers, with the exception of the participant number, will be redacted on the copies of the medical records before submission to Pfizer Safety.
- The investigator will attempt to establish a diagnosis of the event based on signs, symptoms, and/or other clinical information. Whenever possible, the diagnosis (not the individual signs/symptoms) will be documented as the AE or SAE.

Assessment of Intensity

The investigator will make an assessment of intensity for each AE and SAE reported during the study and assign it to 1 of the following categories:

- Mild: A type of AE that is usually transient and may require only minimal treatment or therapeutic intervention. The event does not generally interfere with usual ADL.
- Moderate: A type of AE that is usually alleviated with additional specific therapeutic intervention. The event interferes with usual ADL, causing discomfort, but poses no significant or permanent risk of harm to the research participant.
- Severe: A type of AE that interrupts usual ADL, or significantly affects clinical status, or may require intensive therapeutic intervention.

An event is defined as "serious" when it meets at least 1 of the predefined outcomes as described in the definition of an SAE, NOT when it is rated as severe.

Assessment of Causality

- The investigator is obligated to assess the relationship between study intervention and each occurrence of each AE or SAE. The investigator will use clinical judgment to determine the relationship.
- A "reasonable possibility" of a relationship conveys that there are facts, evidence, and/or arguments to suggest a causal relationship, rather than a relationship cannot be ruled out.

- Alternative causes, such as underlying disease(s), concomitant therapy, and other risk factors, as well as the temporal relationship of the event to study intervention administration, will be considered and investigated.

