#### 6.6.1. Adverse Events

Adverse events will be listed and summarized by treatment and overall, in accordance with sponsor reporting standards using the safety analysis set defined in Section 4.

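### The SAP's treatment-emergent rule has no provision for worsening, so an adverse event open before the first dose that intensifies after it can go unflagged.

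*SAP*

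**What the plan says.** SAP 3.5.1 gives the definition: "An adverse event is considered a Treatment-Emergent Adverse Event (TEAE) if the event started during the effective duration of treatment." It then sets the window, flagging "All events that start on or after the first dosing day and time/start time, if collected, but before the end of the study", and closes with the exclusion: "The algorithm will not consider any events that started prior to the first dose date." Neither this section nor SAP 6.6.1 mentions an increase in intensity.

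SAP 6.6.1 describes the output: "Adverse events will be listed and summarized by treatment and overall, in accordance with sponsor reporting standards." It does not use the term TEAE.

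The protocol supplies the data to which the rule is applied:

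- Section 8.4.1: active collection "begins from the time the participant provides informed consent". Under 8.4.1.2, all events from that point go on the CRF.
- Section 10.3.3: the investigator is to make "an assessment of intensity for each AE and SAE reported during the study and assign it to 1 of the following categories", these being mild, moderate and severe.
- Section 10.3.1: a flare of a pre-existing condition, chronic or intermittent, is an adverse event, "including an increase in either frequency and/or intensity of the condition".

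**The concern.** Safety and tolerability is the primary objective, and Protocol 9.1 rules out formal hypothesis testing. The tabulated counts are therefore the result. A symptom that is mild before dosing and moderate or severe after it is something a first-in-human safety table should show. Under an onset-only rule, whether it is flagged depends on how the site records it: as a new event with a post-dose start, or as an update to the record already open.

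Pre-dose events are possible in practice. Screening normally runs for up to 28 days before the first dose. Participants are in the unit from Day -2 in Period 1 and stop caffeine and nicotine 24 hours before dosing (Protocol 5.3.3). That minor symptoms such as headache begin in this window is plausible, but it is an assumption and not a figure from the documents.

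**Working it through.** The plan states no figure to reproduce. The check is to run the SAP rule over the cases that the protocol allows.

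| Case | How it is recorded | Result under SAP 3.5.1 |
|---|---|---|
| A. Pre-existing condition worsens after dosing | New event with post-dose start, in line with Protocol 10.3.1 | Flagged |
| B. Event opened between consent and Day -1, worsens after dosing | Site opens a new record with post-dose start | Flagged |
| C. Same as B | Site updates the open record | Pre-dose start is kept; not flagged |
| D. Event starts after the Period 1 dose, worsens after a later dose | Either way | Flagged, because the cut-off is the first dose in the study |
| E. Event starts on Day 1 before dosing, worsens after it | Site updates the open record | Not flagged if times are collected; unclear if they are not, because inclusion uses day and time but exclusion uses the date |

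**Which of B and C applies?** The documents do not settle it.

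- Protocol 10.3.3 assigns an intensity to each event and has no rule for a change over time.
- Its follow-up text sends new information to the documents first submitted. That leans towards C, although the line says nothing about start dates.
- The exacerbation clause in 10.3.1 leans towards a new record, but it speaks of chronic or intermittent conditions. It does not clearly reach an acute symptom already open as an adverse event.
- Protocol 10.1.7 places CRF conventions in a separate completion document that is not available here.

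**Does an unflagged event leave the tables?** Only if the tables are restricted to flagged events. SAP 6.6.1 does not say so and defers to sponsor reporting standards, which are also not available. If the tables are not restricted, a different gap appears. An event that began before any dose has no treatment of onset, and the SAP does not say under which treatment its worsening is summarized.

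**Where the exposure lies.** Only onsets between consent and a participant's first dose are affected. If such an event worsens soon after that dose, it belongs to the first-period treatment: about 6 participants on drug and 2 on placebo in each cohort.

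**Scale.** Protocol 9.5 plans about 6 participants on drug per dose level.

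- One participant: 1/6 = 0.167, or 16.7 percentage points.
- Example: a true 2/6 = 33.3% is shown as 1/6 = 16.7%.

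The incidence in a table row falls by this amount only if the participant has no other flagged event in that row.

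**The case against.** The strongest reply is that the harm needs two conditions that the documents do not state: the worsened event keeps its old start date, and the tables show TEAEs only. Protocol 10.3.1 also brings several kinds of worsening in as adverse events. Besides exacerbations, it names clinically significant safety findings that deteriorate from baseline and conditions first detected after dosing, and it exempts fluctuations of pre-existing conditions only if they do not worsen. Laboratory, vital-sign and ECG data have their own period baselines and summaries. The stopping rules in Protocol 6.6.1 rest on severe events, SAEs, abnormalities and exposure, not on the flag.

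Most of this stands. It narrows the gap to case C and to case E, which shares its recording, and it removes any effect on dose-escalation decisions. It does not supply the missing clause.

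A reader might infer three stronger things that the documents do not support:

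- *Pre-dose events are discarded.* The algorithm ignores them for flagging, but they remain on the CRF and SAP 6.6.1 provides listings.
- *Worsened events are left out of the primary safety tables.* SAP 6.6.1 never limits those tables to TEAEs.
- *The error can only understate harm from the drug.* The rule takes no account of treatment or causality. It would also miss a worsened event on placebo, and that would widen the apparent difference between drug and placebo.

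The figure of 1/6 is true of any single event with six participants. It gives scale and is not evidence that the problem occurs.

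**Conclusion.** The concern holds in limited form. SAP 3.5.1 states an onset-only rule with an explicit exclusion. Following it as written, with worsening entered in the open record, misses a pre-dose event that intensifies after dosing. Any table built on the flag would then omit the event, whichever treatment the participant received.

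The size is about 17 percentage points of incidence at a dose level for each affected participant on drug who has no other flagged event in the row. The number of such participants cannot be derived from the documents. It is zero if each worsening becomes a new record.

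The conclusion rests on two assumptions: at least some sites' entries update the open record, and at least some tables use the TEAE flag. No sample size, error rate or stopping decision changes. It is still more than a missing detail, because the SAP states an exclusion for which a better rule is available at almost no cost.

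**What to change.** 1. In SAP 3.5.1, replace the exclusion sentence with: *An AE is treatment-emergent if it starts on or after the first dose, or starts before the first dose and increases in intensity on or after it; a worsened event is attributed to the treatment of the period in which it worsened.* Reword the two onset-only sentences before it to agree, and use date and time throughout so that pre-dose events on Day 1 are handled one way. The attribution clause is needed because each participant has up to four periods.
2. In SAP 6.6.1, state whether the tables show TEAEs or all adverse events.
3. State the CRF convention for a change in intensity, and record the date of worsening for the remaining cohorts. Protocol 4.1 describes Cohort 1 discharges as already past, so use source records for that cohort where available and say in the report where they are not.

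The cost is one SAP sentence with matching edits, one clarification and a CRF completion note. No visit or procedure changes. The downside is that a few background symptoms that happen to worsen will be counted, on both drug and placebo.
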